6.1. DCD Donor Eligibility Criteria

Donor Inclusion Criteria

- Maastricht Category III DCD donor, defined as expected death after the withdrawal of life-supportive therapy (WLST)

- Donor age 18-49 years old inclusive
- Warm ischemic time (WIT) ≤ 30 mins, with warm ischemic time defined as: Time from when mean systolic blood pressure (SBP) is < 50 mmHg or peripheral saturation < 70% to aortic cross-clamp and administration of cold cardioplegia in the donor.

Donor Exclusion Criteria

Donor hearts will be excluded if they meet any of the following criteria:

- Previous cardiac surgery;
- Known coronary artery disease;
- Cardiogenic shock or myocardial infarction;
- Sustained terminal EF of ≤ 50%; or
- Significant valve disease except for competent bicuspid aortic valve.

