The analysis of this endpoint will be performed using a linear probability model, with the following terms in the model: (1) treatment; (2) all of the known donor and recipient risk factors listed previously; and (3) any of the potential risk factors listed above for which there is a statistically significant difference between treatment groups. The p -value for the test of the null hypothesis will be obtained based on a statistic for the difference (SOC - DCD) in least squares means (actually proportions rather than means) for each treatment minus the non-inferiority margin of 0.20 all divided by the standard error of the difference in the least squares means and assuming an approximate normal distribution. The test will be conducted at the 0.05 level of significance.

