## 3.0 STUDY DESIGN

### 3.1 Overview

This is a prospective, randomized and concurrent controlled, non-inferiority pivotal trial in which subjects who receive a DCD donor heart transplant will be compared to subjects who receive a standard of care (SOC) donor heart transplant, regardless of whether those subjects were randomized to receive an SOC donor heart (SOC1) or to potentially receive a DCD donor heart (SOC2). The primary effectiveness comparison between these groups is analyzed by actual treatment and includes adjustment for differences in risk factors. The trial design is illustrated in Figure 1 below.

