### 3.3 Blinding

This is an open label study. However, the SOC 6-month primary endpoint survival data will be blinded to the statistical group until the database hard-lock.

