### 3.4 Determination of Sample Size

We have assumed that transplantation of a DCD donor heart will be an infrequent event and that there will be at least a 1:1 ratio of SOC heart transplants to DCD heart transplants, despite the 3:1 randomization to the ***DCD Heart Possible*** and ***SOC Heart Only*** groups. The sample size calculations were based on the following specifications:

- Non-inferiority study with comparison of DCD heart transplanted recipients to SOC heart transplanted recipients
- Primary endpoint is patient survival at 6 months post-transplant
- One-sided normal approximation test
- Alpha = 0.05
- Power = 80%
- Assume 1:1 occurrence of SOC heart transplants (SOC1 and SOC2) and DCD heart transplants
- True SOC survival percentage = 93%
- True DCD survival percentage = 85%
- Non-inferiority margin = 20%.

Based on these assumptions, a sample size of 84 DCD heart transplanted recipients and at least 84 SOC heart transplanted recipients will provide at least 80% power. This sample size was increased to

90 per group to reflect potential enrollment of subjects who are lost to follow-up, withdraw or do not meet eligibility criteria.

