### 12.1 Primary Effectiveness Endpoint Analyses

The primary effectiveness endpoint is a comparison of survival at the six months post-transplant visit for DCD heart transplanted recipients and standard criteria heart transplanted recipients (SOC1 + SOC2), adjusting for differences in known risk factors. It will be calculated for both the DCD/SOC Heart Transplanted Recipient Populations and the DCD/SOC-mITT Heart Transplanted Recipient Populations, with the comparison of the DCD Heart Transplanted Recipient Population vs. the SOC Heart Transplanted Recipient Population considered the primary analysis. This is a non-inferiority study.

We will adjust for the known donor and recipient risk factors for mortality shown in the list below:

Donor Variables:

- Donor age  $\geq$  55 years
- Ischemic Time  $\geq$  4 hours
- Gender mismatch (female donor to male recipient).

Recipient Variables:

- Recipient age  $\geq$  65 years
- MCS (including LVAD, RVAD, BiVAD, ECMO, TAH, or IABP) prior to transplant
- Mechanical ventilation at time of transplant

The null and alternative hypotheses for the primary endpoint are as follows:

$$H_0: p_{SOC} - p_{DCD} \geq 0.20$$

vs.

$$H_1: p_{SOC} - p_{DCD} < 0.20$$

where  $p_{DCD}$  and  $p_{SOC}$  represent the true survival proportions at the six months follow-up visit for DCD and SOC heart transplant patients, respectively.

The primary analysis of this endpoint will be performed using a linear probability model, with the following terms in the model: (1) treatment; and (2) the known donor and recipient risk factors listed above. Variables that make the model fail to converge (e.g., due to quasi-complete separation of datapoints) will be dropped from the model. The p-value for the test of the null hypothesis will be obtained based on a statistic for the difference (SOC - DCD) in least squares mean proportions for each treatment minus the non-inferiority margin of 0.20 all divided by the standard error of the difference in the least squares mean proportions and assuming an approximate normal distribution. The test will be conducted at the one-sided 0.05 level of significance. Additionally, this endpoint will be summarized by treatment group using counts

and percentages, and an exact (Clopper-Pearson) 95% confidence interval for the percentages will be presented.

Generalized SAS code to implement this analysis is given below:

```
ods output diffss=diffss lsmeans=lsmeans;
proc genmod descending;

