  class trt01a (ref='DCD');
  model survival=trt01a riskfactors / dist=binomial link=identity;
  lsmeans trt01a / diff cl alpha=0.1;
run;

data diffss;
  set diffss;
  pvalue=put(probnorm((estimate - 0.20)/stderr), 6.4));
run;
```

Per FDA's request, a sensitivity analysis will be performed to compare the DCD Heart Possible Population vs the SOC Only Population, i.e. (DCD + SOC2) vs SOC1. Also at FDA's request, an additional sensitivity analysis will repeat the primary effectiveness analysis with the same non-inferiority margin but without adjustment for covariates. Finally, assuming the primary analysis results demonstrate non-inferiority of OCS to SOC, a tipping point analysis (without risk factor adjustment) will be performed using the Wald method, in which SOC subjects categorized as having an unsuccessful 6-month survival outcome will be iteratively imputed as having a successful survival outcome. The "tipping point" is the number of SOC subjects needed to be imputed as having successful outcomes in order to no longer reject the null hypothesis of inferiority.

An additional analysis of the primary endpoint will evaluate pooling by recipient investigational site. This analysis will be performed on observed data for both the DCD/SOC Heart Transplanted Recipient Populations and the DCD/SOC-mITT Heart Transplanted Recipient Populations. A logistic regression model will be fit with all terms included in the primary effectiveness analysis, site, and the interaction of site with treatment. The p-values for site and the treatment by site interaction term in the model will be presented, with statistical significance defined at the  $\alpha = 0.15$  level. Sites with  $\leq 10$  subjects will be pooled for this analysis.

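### SAP 12.1 drops variables that make the primary model fail to converge, but gives no removal order and does not say whether a boundary fit counts as failure; at the planned number of deaths a boundary fit is the usual case

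*SAP*

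**What the plan says.** SAP 12.1 calls the primary analysis a linear probability model and codes it as "model survival=trt01a riskfactors / dist=binomial link=identity". The terms are treatment and six yes/no factors: donor age 55 or over, ischemic time of 4 hours or more, female donor to male recipient, recipient age 65 or over, mechanical circulatory support (MCS) before transplant, and ventilation at transplant. The only instruction for a difficult fit is: "Variables that make the model fail to converge (e.g., due to quasi-complete separation of datapoints) will be dropped from the model". SAP 5.2 repeats the model without any such rule.

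Protocol 10.3.1 puts "all of the known donor and recipient risk factors listed previously" in the model and has no drop rule, so the rule is a SAP addition.

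SAP 3.1 explains why adjustment matters: "The primary effectiveness comparison between these groups is analyzed by actual treatment and includes adjustment for differences in risk factors". SAP 3.3 says that "the SOC 6-month primary endpoint survival data will be blinded to the statistical group until the database hard-lock". SAP 12.1 also plans a comparison by randomized arm, and says that "an additional sensitivity analysis will repeat the primary effectiveness analysis with the same non-inferiority margin but without adjustment for covariates".

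**The concern.** The rule leaves three things open: which variable goes first, how the responsible variable is identified, and whether a fit that ends at a fitted survival of exactly 1 has failed. Its example, quasi-complete separation, is mainly a logistic-regression problem. An identity-link binomial fit runs into trouble when a fitted probability reaches 0 or 1, so the example does not say what triggers removal here.

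The contrast is by treatment received. SOC2 patients are those in the DCD Heart Possible arm for whom an SOC heart came first (SAP 3.2), so randomization does not protect the comparison and the risk adjustment has to support it. Whether the model converges can be known only once SOC survival is available, after hard-lock. If the rule is triggered, the adjustment set is chosen with outcomes visible.

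**Working it through.** **Inputs from the documents.** SAP 3.4: SOC survival 93%, "True DCD survival percentage = 85" (per cent), margin 20 points, one-sided alpha 0.05, power 80%, 84 per group raised to 90. SAP 3.5: 90 + 90 analysed. SAP 12.1: intercept, treatment and six factors, which is eight parameters. Protocol 6.1: "Donor age 18-49 years old inclusive" for DCD donors, so donor age 55 or over can occur only in the SOC group.

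**1. The plan's own sample size.** n = (1.645 + 0.842)² × (0.93×0.07 + 0.85×0.15) / (0.20 − 0.08)² = 6.18 × 0.1926 / 0.0144 ≈ 83 per group, against 84 stated. Power is 80.5% at 84 and 82.9% at 90. The figure is reproduced; it is for the unadjusted contrast.

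**2. Expected deaths.** 90×0.07 + 90×0.15 = 6.3 + 13.5 = 19.8.

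**3. Why the maximum reaches a boundary.** Fitted mortality is a sum of coefficients and must stay between 0 and 1 for every observed pattern. If no patient exposed to a factor died, lowering that factor's coefficient always raises the likelihood, until some exposed pattern has a fitted survival of 1. Two examples with assumed prevalences:
- Ventilation at 2%: 180×0.02 = 3.6, about 4 exposed. Average mortality is 19.8/180 = 0.11, so the chance of no death is 0.89⁴ = 0.63.
- Donor age 55 or over at 5% of SOC: 90×0.05 = 4.5 exposed. The chance of no death is 0.93⁴ = 0.75 or 0.93⁵ = 0.70.

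Treated as independent, at least one of these two factors has no deaths with probability about 1 − 0.37×0.25 = 0.91.

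**4. Simulation set-up.** The documents give no factor prevalences, so they were assumed (%, SOC/DCD where they differ):

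| Set | Donor ≥55 | Ischemia ≥4 h | Mismatch | Age ≥65 | MCS | Ventilated |
|---|---|---|---|---|---|---|
| A | 5/0 | 15/30 | 15 | 20 | 60 | 2 |
| B | 5/0 | 20/60 | 15 | 20 | 60 | 2 |
| C | 2/0 | 10 | 10 | 15 | 40 | 1 |
| D | 8/0 | 25 | 25 | 25 | 50 | 5 |
| E | 5/0 | 20/90 | 15 | 20 | 60 | 2 |

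Mortality = b0 + delta×DCD + e×(number of factors), with SOC mean 7%, delta 0.08 (planning) or 0.20 (null), and e = 0 or 0.05.

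**5. Boundary rate.**
- Sets A-E at 93/85: 97-99% with six factors, 75-91% with the four common ones (ischemia, mismatch, age, MCS), and 0-0.3% with treatment only.
- Other prevalence sets, risk models and solvers: 93-100% with six factors. Removing factors with no deaths first still left 85-95% at a boundary, so rare factors are not the whole cause.
- Away from the planning case: 77% with 15% mortality in both groups (27 deaths), and 40% with two factors only.

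**6. If a boundary fit counts as failure** (93/85).
- One-at-a-time removal, averaged over all 720 orders: 1.0-1.9 of six factors kept. The treatment-only model is reached in 21-44% of trial-order combinations. A single trial leads to a median of 8-18 different final sets.
- Largest subset with an interior fit: 2.9-3.7 factors kept, none in 0-1% of trials.
- Two removal orders give different verdicts in about 1-14% of trials. At least one of the 720 orders differs from the others in 6-35%.

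**7. If a boundary fit is accepted** (sets A and C). All six factors stay. The true sampling SD of the difference was 0.047-0.052. The mean Wald SE was 0.055-0.064 with observed information (6-30% too large) and 0.037-0.039 with expected information (17-26% too small). The largest estimated difference that passes is 0.20 − 1.645×SE. This is 0.20 − 0.105 = 0.095 at SE 0.064 and 0.20 − 0.061 = 0.139 at SE 0.037.

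**The case against.** The strongest reply is that the rule acts only on a failure to converge, and a boundary maximum is not the same as a software failure. If the procedure accepts the boundary fit, no factor is dropped. That stands: SAS was not run and the branch is unknown. The accepted fit, however, carries the standard-error problem in step 7.

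Second, the one-or-two-factor figure comes from removing factors one at a time in arbitrary order, which the SAP does not prescribe. Removing only the variables responsible can be read as keeping the largest fittable subset, about three factors. This also stands, although the retained set would still depend on outcomes.

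Third, sets B and E give DCD hearts long ischemic times. Protocol 8.1 records cold ischemia before and after OCS, and SAP 10.0 lists OCS perfusion time and ischemic time separately, so that alignment with treatment is less likely. A set with about 1% DCD exposure still gave 99% boundary fits, so the main result does not rest on it.

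Fourth, the starting factors, margin, alpha and test statistic are fixed, and the unadjusted and as-randomized analyses are planned. This limits the damage, but neither analysis is the risk-adjusted result that the SAP names as primary.

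A reader might also infer that the SAP contradicts the protocol's instruction to include all known factors. It does not: the rule is an added contingency.

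**Conclusion.** The concern holds in conditional form. The missing order and missing boundary definition are plain in the text. At 19.8 expected deaths the ambiguity would matter in about 93-100% of simulated trials under every assumed prevalence set. Both branches are poor: covariates removed according to outcomes after unblinding, or a test that divides by an unreliable standard error.

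Two stronger readings are tempting and not supported. One is that the adjusted primary analysis will collapse to one or two factors or to none; that needs a boundary fit to count as failure and a particular removal procedure. The other is that the trial's conclusion is generally at risk; a pair of removal orders disagrees in only about 1-14% of trials.

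Confidence is high for the gap and the boundary rate. It is lower for the retained-factor counts, which rest on assumed prevalences and assumed analyst behaviour. This should be fixed before lock; it is not fatal to the design.

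**What to change.** **Preferred.** Fit the linear probability model by ordinary least squares with HC3 robust standard errors. Keep the same LS-mean difference, the 0.20 margin and the one-sided 0.05 z-test. Replace the drop sentence with an outcome-blind rule, for example: a factor with fewer than 5 exposed patients in both groups combined, counted before SOC survival is unblinded, is omitted; no factor is removed for any reason that uses outcomes.

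In simulation with this rule the model could be fitted in all 80,000 trials, kept 4.1-5.8 factors, and had type I error of 4.6-5.6%. The threshold is a choice but matters little: requiring 5 exposed in each group gave 4.7-6.0%.

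**Cost.** SAP wording and a few lines of code. Individual fitted values may exceed 1. Very sparse factors may be omitted: donor age 55 or over is kept in 3-86% of trials, depending on the set. Adjusted power is about 72-83% under most assumed prevalences. It falls to 53-59% in set E, where ischemic time is strongly aligned with treatment; that loss comes from adjusting for such a factor, not from least squares.

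**Minimum, if the binomial fit is kept.** Pre-specify the removal order, the boundary criterion and the treatment-only model as the last step. This makes the result reproducible but does not remove the dependence on outcomes. With the least-exposed factor removed first, 1.6-2.4 factors were kept on average, none in 8-26% of trials, and the kept set still changed when only the deaths were redrawn.

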## 12.2 Secondary Effectiveness Endpoint Analyses

The primary analysis of the secondary effectiveness endpoint is the utilization rate based on the OCS Heart Population, defined in Section 4.2. This endpoint will be summarized for the OCS Heart Population using counts and percentages and an exact (Clopper-Pearson) 95% confidence interval for the true percentage based on the binomial distribution. It will also be summarized for the modified OCS Heart Population, defined as the number of DCD hearts that were successfully transplanted after preservation and assessment on the OCS divided by the total number of DCD donor hearts that were instrumented on the OCS.

### 12.3 Other Effectiveness Endpoints Analyses

Other endpoints collected for the DCD and DCD-mITT Heart Transplanted Recipient Populations include:

- Use of post-transplant MCS (includes LVAD, RVAD, BiVAD, ECMO, TAH, or IABP) for > 72 hours immediately post-transplant. To clarify, pre-transplant IABP (regardless of indication) that is removed per standard of care a couple of days post-transplant will be excluded from any post-transplant MCS analysis. The pre-transplant IABP that is maintained during transplantation and restarted for post-transplant cardiac support, and the IABP placed post-transplantation will be considered as newly placed IABP. Only the post-transplant MCS initiated within the initial 24 hours (T24 visit) post-transplant with a duration of use greater than 72 hours will be considered to meet this study endpoint. In cases where a recipient received more than one type of post-transplant support, the support type with the longest continuous duration will be used.

Other endpoints collected for both the DCD heart transplanted recipients and the SOC heart transplanted recipients (SOC1+SOC2) include:

- Patient and graft survival at 30 days post-transplant
- Patient and graft survival at 30 days or initial hospital discharge, if later than 30 days
- Moderate-severe PGD (left or right ventricle) (not including rejection or cardiac tamponade) according to ISHLT consensus manuscript (as defined in Appendix 1 of the protocol) within 24 hours post-transplant
- Severe PGD (left or right ventricle) (not including rejection or cardiac tamponade) according to ISHLT consensus manuscript (as defined in Appendix 1 of the protocol) within 24 hours post-transplant
- Patient survival assessed at the 12 months post-transplant follow-up visit
- Patient and graft survival at 30, 180, and 365 days post-transplant estimated by Kaplan Meier method

Each endpoint, except Kaplan-Meier estimates, will be summarized using counts and percentages and an exact (Clopper-Pearson) 95% confidence interval for the true percentage based on the binomial distribution.

Kaplan-Meier estimates for patient survival and graft survival (graft failure includes heart re-transplant and cardiac graft-related death) probabilities will be calculated for the SOC Heart Transplanted Recipient Population, the SOC-mITT Heart Transplanted Recipient Population, the DCD Heart Transplanted Recipient Population, and the DCD-mITT Heart Transplanted Recipient Population for the following time points: Day 30, Month 6, and Month 12. Of note, the Kaplan-Meier estimates will consider time as a continuous variable measured in days. The Month 6 and Month 12 timepoints will be considered to be 180 and 365 days post-transplantation, respectively. Re-transplanted patients will be censored at the day of re-transplantation. The estimated difference in survival probability (SOC – DCD) and its 90% confidence interval will also be presented at each of the three time points.

